9.4 Abnormal Test Findings

The criteria for determining whether an abnormal objective test finding should be reported as an adverse event are as follows:

CONFIDENTIAL

- Test result is associated with accompanying symptoms, and/or
- Test result requires additional diagnostic testing or medical/surgical intervention, and/or
- Test result leads to a change in trial dosing (outside of protocol-stipulated dose adjustments) or discontinuation from the trial, significant additional concomitant drug treatment, or other therapy, and/or
- Test result is considered to be an adverse event by the investigator or sponsor.

Merely repeating an abnormal test, in the absence of any of the above conditions, does not constitute an adverse event. Any abnormal test result that is determined to be an error does not require reporting as an adverse event.

9.5 Serious Adverse Events

A serious adverse event is any untoward medical occurrence at any dose that:

- Results in death;
- Is life-threatening (immediate risk of death);
- Requires inpatient hospitalization or prolongation of existing hospitalization;
- Results in persistent or significant disability/incapacity;
- Results in congenital anomaly/birth defect.

Progression of the malignancy under trial (including signs and symptoms of progression) should not be reported as a serious adverse event unless the outcome is fatal within the safety reporting period. Hospitalization due to signs and symptoms of disease progression should not be reported as serious adverse event. If the malignancy has a fatal outcome during the trial or within the safety reporting period, then the event leading to death must be recorded as an adverse event and as a serious adverse event with CTC grade 5 (see Section 9.7, Severity Assessment).

Medical and scientific judgment is exercised in determining whether an event is an important medical event. An important medical event may not be immediately life-threatening and/or result in death or hospitalization. However, if it is determined that the event may jeopardize the patient or may require intervention to prevent one of the other outcomes listed in the definition above, the important medical event should be reported as serious.

Examples of such events are intensive treatment in an emergency room or at home for allergic bronchospasm; blood dyscrasias or convulsions that do not result in hospitalization; or development of drug dependency or drug abuse.

The Sponsor will notify the FDA of any adverse experience associated with the use of the drug that is both serious and unexpected, as soon as possible and in no event later than 15 calendar days after the PI's discovery of the event. Notification may be submitted to the Sponsor on a MedWatch Form FDA 3500A <http://www.fda.gov/medwatch/safety/3500a.pdf>.

The PI shall also notify the Sponsor of any unexpected fatal or life-threatening experiences associated with the use of the drug, as soon as possible but no later than 7 calendar days from the PI's discovery of the event information.

The serious adverse event report must include, but need not be limited to: (1) the date of the event; (2) designation of the report as an initial report or a follow-up report, (3) identification of all safety reports previously filed for the clinical protocol concerning a similar adverse event, and an analysis of the significance of the adverse event in light of previous similar reports; (4) clinical site; (5) the Principal Investigator; (6) NIH Protocol number; (7) FDA's Investigational New Drug (IND) Application number; (8) vector type , e.g., adenovirus; (9) vector subtype, e.g., type 5, relevant deletions; (10) gene delivery method, e.g., *in vivo*, *ex vivo* transduction; (11) route of administration, e.g., intratumoral, intravenous; (12) dosing schedule; (13) a complete description of the event; (14) relevant clinical observations; (15) relevant clinical history; (16) relevant tests that were or are planned to be conducted; (17) date of any treatment of the event; and (18) the suspected cause of the event. These items may be reported by using the recommended Adverse Event Reporting Template available on NIH OBA's web site at: <http://www4.od.nih.gov/oba/rac/documents1.htm>, or you can use a MedWatch form.

9.6 Hospitalization

Adverse events reported from clinical trials associated with hospitalization or prolongation of hospitalization is considered serious. Any initial admission (even if less than 24 hours) to a healthcare facility meets these criteria. Admission also includes transfer within the hospital to an acute/intensive care unit (e.g., from the psychiatric wing to a medical floor, medical floor to a coronary care unit, neurological floor to a tuberculosis unit).

Hospitalization does not include the following:

- Rehabilitation facilities;
- Hospice facilities;
- Respite care (e.g., caregiver relief);
- Skilled nursing facilities;
- Nursing homes;
- Routine emergency room admissions;
- Same day surgeries (as outpatient/same day/ambulatory procedures).

Hospitalization or prolongation of hospitalization in the absence of a precipitating, clinical adverse event is not in itself a serious adverse event. Examples include:

- Admission for treatment of a preexisting condition not associated with the development of a new adverse event or with a worsening of the preexisting condition (e.g., for work-up of persistent pre-treatment lab abnormality);

- Social admission (e.g., patient has no place to sleep);
- Administrative admission (e.g., for yearly physical exam);
- Protocol-specified admission during a clinical trial (e.g., for a procedure required by the trial protocol);
- Optional admission not associated with a precipitating clinical adverse event (e.g., for elective cosmetic surgery);
- Hospitalization for observation without a medical AE;
- Pre-planned treatments or surgical procedures should be noted in the baseline documentation for the entire protocol and/or for the individual patient;
- Admission exclusively for the administration of blood products.

Diagnostic and therapeutic non-invasive and invasive procedures, such as surgery, should not be reported as adverse events. However, the medical condition for which the procedure was performed should be reported if it meets the definition of an adverse event. For example, an acute appendicitis that begins during the adverse event reporting period should be reported as the adverse event, and the resulting appendectomy should be recorded as treatment of the adverse event.

9.7 Severity Assessment

If required on the adverse event case report forms, the investigator will use the following definitions of Severity in accordance with Cancer Therapy Evaluation Program, Common Terminology Criteria for Adverse Events (Version 4.03) to describe the maximum intensity of the adverse event. If the event is serious, the CTC grade reported in the adverse event CRF must be consistent with the description of CTC grade included in the narrative section of the serious adverse event report.

Table 8.1: General AE Grading Assessment

Grade	Clinical Description of Severity
0	No change from normal or reference range (This grade is not included in CTCAE but may be used in certain circumstances)
1	MILD adverse event
2	MODERATE adverse events
3	SEVERE adverse events
4	LIFE-THREATENING OR DISABLING adverse events
5	DEATH RELATED TO adverse events

Note the distinction between the severity and the seriousness of an adverse event. A severe event is not necessarily a serious event. For example, a headache may be severe (interferes significantly with patient's usual function) but would not be classified as serious unless it met one of the criteria for serious adverse events, listed above.

9.8 Causality Assessment

The investigator's assessment of causality must be provided for all adverse events (serious and non-serious). An investigator's causality assessment is the determination of whether there exists a reasonable possibility that the investigational product caused or contributed to an adverse event. If the investigator's final determination of causality is unknown and the investigator does not know whether or not investigational product caused the event, then the event will be handled as "related to investigational product" for reporting purposes. If the investigator's causality assessment is "unknown but not related to investigational product", this should be clearly documented on trial records.

In addition, if the investigator determines a serious adverse event is associated with trial procedures, the investigator must record this causal relationship in the source documents and CRF, as appropriate, and report such an assessment in accordance with the serious adverse event reporting requirements, if applicable.

9.9 Exposure *in utero*

An exposure in-utero (EIU) occurs if:

1. A female becomes, or is found to be, pregnant either while receiving or having been directly exposed to (e.g., environmental exposure) the investigational product, or the female becomes, or is found to be, pregnant after discontinuing and/or being directly exposed to the investigational product (maternal exposure);
2. A male has been exposed, either due to treatment or environmental, to the investigational product prior to or around the time of conception and/or is exposed during the partner pregnancy (paternal exposure).

If a woman becomes pregnant or suspects that she is pregnant while participating in this study, she must inform the investigator immediately and permanently discontinue study drug.

Oncoceutics must be immediately (with 24 hours of awareness) be contacted. The pregnancy must be followed for the final pregnancy outcome.

If any trial patient or trial patient's partner becomes or is found to be pregnant during the trial patient's treatment with the investigational product, the investigator must submit this information to Oncoceutics. In addition, the investigator must submit information regarding environmental exposure to this study drug in a pregnant woman (e.g., a nurse reports that she is pregnant and has been exposed to a cytotoxic product by inhalation or spillage). This must be done irrespective of whether an adverse event has occurred and within 24 hours of awareness of the pregnancy. The information submitted should include the anticipated date of delivery (see below for information related to induced termination of pregnancy).

Follow-up is conducted to obtain pregnancy outcome information on all Exposure in Utero reports with an unknown outcome. The investigator will follow the pregnancy until completion or until pregnancy termination (i.e., induced abortion) and then notify Oncoceutics of the outcome. The reason(s) for an induced abortion should be specified. A serious adverse event case is created with the event of ectopic pregnancy.

CONFIDENTIAL

9.10 Withdrawal Due to Adverse Events

Withdrawal due to adverse event should be distinguished from withdrawal due to insufficient response, according to the definition of adverse event noted earlier, and recorded on the appropriate adverse event CRF page. When a patient withdraws due to a serious adverse event, the serious adverse event must be reported in accordance with the reporting requirements defined below.

9.11 Eliciting Adverse Event Information

The investigator is to report all directly observed adverse events and all adverse events spontaneously reported by the trial patient. In addition, each trial patient will be questioned about adverse events.

9.12 Reporting Requirements

Each adverse event is to be assessed to determine if it meets the criteria for serious adverse event. If a serious adverse event occurs, expedited reporting will follow local and international regulations, as appropriate.

All adverse events will be reported on the adverse event page(s) of the CRF. It should be noted that the form for collection of serious adverse event information is not the same as the adverse event CRF. Where the same data are collected, the forms must be completed in a consistent manner. For example, the same adverse event term should be used on both forms. Adverse events should be reported using concise medical terminology on the CRFs as well as on the form for collection of serious adverse event information.

9.12.1 Serious Adverse Event Reporting Requirements

If a serious adverse event occurs, Oncoceutics is to be notified within 24 hours of awareness of the event by the investigator. In particular, if the serious adverse event is fatal or life-threatening, notification to Oncoceutics must be made immediately, irrespective of the extent of available adverse event information. This timeframe also applies to additional new information (follow-up) on previously forwarded serious adverse event reports as well as to the initial and follow-up reporting of Exposure in Utero and exposure during breast feeding cases.

In the rare event that the investigator does not become aware of the occurrence of a serious adverse event immediately (e.g., if an outpatient trial patient initially seeks treatment elsewhere), the investigator is to report the event within 24 hours after learning of it and document the time of his/her first awareness of the adverse event. For all serious adverse events, the investigator is obligated to pursue and provide information to Oncoceutics in accordance with the timeframes for reporting specified above. In addition, an investigator may be requested by Oncoceutics to obtain specific additional follow-up information in an expedited fashion. This information collected for serious adverse events is more detailed than that captured on the adverse event case report form. In general, this will include a description of the adverse event in sufficient detail to allow for a complete medical assessment of the case and

independent determination of possible causality. Information on other possible causes of the event, such as concomitant medications and illnesses must be provided. In the case of a patient death, a summary of available autopsy findings must be submitted as soon as possible to Oncoceutics or its designated representative.

9.12.2 Potential Cases of Drug-Induced Liver Injury

While ONC201 is not expected to cause significant elevations in liver enzymes, such occurrence is of special interest to regulatory agencies. Abnormal values in aspartate transaminase (AST) and/or alanine transaminase (ALT) concurrent with abnormal elevations in total bilirubin that meet the criteria outlined below in the absence of other causes of liver injury are considered potential cases of drug-induced liver injury (potential Hy's Law cases) and should always be considered important medical events.

The threshold of laboratory abnormalities for a potential case of drug-induced liver injury depends on the subject's individual baseline values and underlying conditions. Subjects who present with the following laboratory abnormalities should be evaluated further to definitively determine the etiology of the abnormal laboratory values:

- A. Subjects with AST or ALT baseline values within the normal range who subsequently present with AST or ALT ≥ 3 times the upper limit of normal concurrent with a total bilirubin ≥ 2 times the upper limit of normal with no evidence of hemolysis and an alkaline phosphatase ≥ 2 times the upper limit of normal or not available.
- B. Subjects with pre-existing AST or ALT baseline values above the normal range who subsequently present with AST or ALT ≥ 2 times the baseline values and ≥ 3 times the upper limit of normal, or ≥ 8 times the upper limit of normal (whichever is smaller) concurrent with a total bilirubin of ≥ 2 times the upper limit of normal and increased by one upper limit of normal over baseline or >3 times the upper limit of normal (whichever is smaller) with no evidence of hemolysis and an alkaline phosphatase ≥ 2 times the upper limit of normal or not available.

The subject should return to the investigational site and be evaluated as soon as possible, preferably within 48 hours from awareness of the abnormal results. This evaluation should include laboratory tests, detailed history and physical assessment and the possibility of hepatic neoplasia (primary or secondary) should be considered. In addition to repeating AST and ALT, laboratory tests should include albumin, creatine kinase, total bilirubin, direct and indirect bilirubin, gamma-glutamyl transferase (GGT), international normalized ratio (INR) and alkaline phosphatase. A detailed history, including relevant information, such as review of ethanol, recreational drug and supplement consumption, family history, sexual history, travel history, history of contact with a jaundiced subject, surgery, blood transfusion, history of liver or allergic disease, and work exposure, should be collected. Further testing for acute hepatitis A, B, or C infection and liver imaging (e.g., biliary tract) may be warranted. All cases confirmed on repeat testing as meeting criteria A or B, with no other cause for LFT abnormalities identified at the

time should be considered potential Hy's Law cases irrespective of availability of all the results of the investigations performed to determine etiology of the abnormal LFTs. Such potential Hy's Law cases should be reported as serious adverse events.

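### Liver-injury criteria A and B in 9.12.2 require a high alkaline phosphatase; the sign appears reversed, so an otherwise qualifying patient with a measured value below 2 × ULN misses the evaluation and SAE trigger

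*Combined protocol and SAP*

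**What the plan says.** Section 9.12.2 opens by describing the laboratory picture it seeks: "Abnormal values in aspartate transaminase (AST) and/or alanine transaminase (ALT) concurrent with abnormal elevations in total bilirubin". When this picture satisfies criterion A or B and nothing else explains the liver injury, the patient is a potential Hy's Law case. Such cases "should always be considered important medical events".

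Criterion A covers patients with normal baseline AST or ALT, and criterion B those with raised baseline values. Their transaminase and bilirubin thresholds differ, but both exclude hemolysis and both then add the same requirement: "an alkaline phosphatase ≥ 2 times the upper limit of normal or not available".

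A patient who meets a criterion should return to the site for evaluation, "preferably within 48 hours from awareness of the abnormal results". The repeat tests include "international normalized ratio (INR) and alkaline phosphatase". The last step applies to "All cases confirmed on repeat testing as meeting criteria A or B" when the work-up has so far shown no alternative cause: these are potential Hy's Law cases and go forward as SAE reports.

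**The concern.** The ALP clause is joined by 'and' to the other conditions. Whenever ALP is measured, a value of at least 2 × ULN is therefore needed to enter the pathway. A patient with raised transaminases and bilirubin, no hemolysis and a normal ALP is left out, which does not fit a section looking for liver injury with no other explanation.

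Three protocol-directed steps depend on this clause: the prompt evaluation, the important-medical-event designation, and the SAE report of confirmed cases. The SAE report in turn brings the 24-hour sponsor notification of 9.12.1.

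The timing of routine tests adds to the concern. After cycle 1, the Schedule of Activities places serum chemistry on day 1 of each 21-day cycle, while 7.3 continues dosing on days 8 and 15. Without the prompt return visit, the next scheduled liver tests may be about three weeks away.

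**Working it through.** The plan gives no figure to reproduce here. The check is of logic, in two parts.

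**1. What the printed sign does**

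Inputs from criterion A: AST or ALT ≥ 3 × ULN; total bilirubin ≥ 2 × ULN; no hemolysis; ALP ≥ 2 × ULN or not available. All four must hold.

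Illustrative patient (assumed values): normal baseline, ALT 5 × ULN, bilirubin 3 × ULN, no hemolysis. The first three conditions hold (5 ≥ 3, 3 ≥ 2, no hemolysis), so ALP alone decides.

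| ALP (× ULN) | Printed: ≥ 2 or missing | If < 2 or missing | If ≤ 2 or missing |
|---|---|---|---|
| 0.8 | not met | met | met |
| 1.5 | not met | met | met |
| 2.0 | met | not met | met |
| 3.0 | met | not met | not met |
| missing | met | met | met |

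Criterion B carries the identical ALP clause. A patient who satisfies its other conditions shows the same pattern.

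SAE status also needs confirmation on repeat testing. With ALT and bilirubin unchanged and the criterion required at both tests:

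| ALP first, then repeat (× ULN) | Printed | < 2 | ≤ 2 |
|---|---|---|---|
| 0.8, 0.8 | not confirmed | confirmed | confirmed |
| missing, 0.8 | not confirmed | confirmed | confirmed |
| missing, 3.0 | confirmed | not confirmed | not confirmed |
| 3.0, 3.0 | confirmed | not confirmed | not confirmed |

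The allowance for a missing ALP gives little relief. ALP is on the same routine chemistry panel as AST, ALT and bilirubin (Schedule of Activities, footnote 13) and is measured again on the repeat panel. A patient who enters with ALP missing and then shows a normal value is not confirmed.

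**2. Which direction was probably meant**

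- *Missing against normal.* A missing ALP qualifies and a measured normal ALP disqualifies. This is coherent if a high ALP is meant to exclude a case, because an absent result then cannot exclude anyone. It is hard to explain if a high ALP is a required finding.
- *Neighbouring condition.* The clause is paired with the absence of hemolysis, which removes a competing explanation. An upper bound on ALP would do the same kind of work.
- *Opening sentence.* The picture described is abnormal transaminases with raised bilirubin and no other cause. A raised ALP is not named as part of it.

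**The case against.** The strongest objection is that the reversal is not proved.

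- Letting a missing value qualify could be a precautionary default under the printed sign.
- The opening sentence defers to criteria A and B. It does not mention hemolysis either, so its silence on ALP is weak evidence.
- Nowhere do the documents say that a high ALP counts as another cause.
- An error in the text of the PDF cannot be fully excluded. Section 5.6, for instance, gives the febrile neutropenia temperature with no comparison sign.

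Much of this is fair, and the direction remains an inference. But a precautionary default does not explain why a measured normal ALP should remove a patient with raised transaminases and bilirubin from a Hy's Law screen. A misread sign is unlikely: it is the same in both criteria, and ≤ appears correctly in the inclusion criteria of the synopsis and 4.1.

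A second objection is that other rules catch these patients. They do so in part:

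- A possibly related Grade 3 or higher non-hematologic event in the first 21 days is generally a DLT (5.6).
- A drug-attributable Grade 3 or 4 event leads to a hold with at least weekly monitoring (section 6).
- A result that needs further diagnostic work is an adverse event (9.4).
- Unknown causality is handled as related (9.8).
- The investigator may judge the event serious (9.5).

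None of these restores the 48-hour visit or the automatic SAE report, and the DLT route ends at day 21. The 48-hour timing is itself only a preference, which limits what is lost.

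A third objection is that reversing the sign takes high-ALP patients out of the automatic trigger. That is true and is a real cost. Removing ALP from the entry conditions would avoid it, since the work-up already looks for other causes.

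**Conclusion.** The concern holds. As printed, an otherwise qualifying patient with a measured ALP below 2 × ULN meets neither A nor B and falls outside the section's evaluation, designation and SAE steps. The same patient with no ALP result can enter. This follows directly from the text, and no other section restores the trigger.

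That the sign is reversed is a well-supported inference, held with medium confidence. It assumes that the printed sign is the one in the source document and that the clause was meant to exclude another explanation.

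The effect is confined to safety evaluation and reporting; the overall response rate and the 10.3 stopping rule do not change. No probability can be attached, because the documents give no rate for such events. The sponsor should correct it, because the change is small and it concerns a patient-safety threshold.

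**What to change.** Check the sign against the source document. Then, in both A and B, change the ALP condition to: < 2 times the upper limit of normal (or ≤ 2 times, whichever the source supports), or not available. The two versions differ only at exactly 2 × ULN.

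The cost is one sign in two sentences and possibly a few more liver evaluations. Patients with ALP at or above 2 × ULN (above 2 × ULN under the ≤ version) would leave the automatic trigger and rely on the general adverse event and SAE rules.

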5.6 Dose Limiting Toxicity (DLT) definition

Toxicity will be evaluated according to the NCI CTCAE, version 4.03. The DLT safety observation window is defined as the first 3 weeks (one cycle). A DLT will be defined as any of the following AEs, occurring within the first 21 days of dosing and considered possibly related (except where defined) to ONC201:

Hematologic:

- Grade 4 neutropenia that persists for >7 consecutive days
- Febrile neutropenia (defined as neutropenia \geq Grade 3 and a body temperature 38.5°C)
- Grade \geq 3 neutropenic infection
- Grade 4 thrombocytopenia (platelets $<25,000$ cells/mm 3) or Grade \geq 3 thrombocytopenia with bleeding

Nonhematologic:

- Any other Grade \geq 3 toxicity not classified under CTCAE blood or bone marrow with the exception of nausea, vomiting, or diarrhea. Grade 3 nausea or vomiting that persists for 5 days and is not controlled with standard antiemetic therapy will be considered a DLT.
- Alopecia is not a DLT
- Any AE leading to inability to complete planned study drug during the DLT window should be considered a DLT

Although toxicities may be observed at any point during treatment, only those occurring during the defined DLT observation window of treatment (1 cycle) that are considered DLTs will guide dose escalation decisions, expansion of a dose level, or evaluation of intermediate dose levels. Patients will be monitored through all cycles of therapy for treatment-related toxicities, and all toxicities, including those occurring in beyond the DLT observation window will be monitored.

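### A confirmed potential Hy's Law case must be reported as serious, but if graded 2 it triggers no hold and counts as a DLT only if a cycle 1 dose is missed

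*Combined protocol and SAP*

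**What the plan says.** **Section 9.12.2.** Criterion A, for patients with normal baseline AST/ALT, requires "AST or ALT ≥ 3 times the upper limit of normal concurrent with a total bilirubin ≥ 2 times the upper limit of normal". Two side conditions on other laboratory findings are then attached to it: "with no evidence of hemolysis and an alkaline phosphatase ≥ 2 times the upper limit of normal or not available". Criterion B adjusts the AST/ALT and bilirubin limits for patients with raised baseline AST/ALT. The patient should be re-evaluated "preferably within 48 hours from awareness of the abnormal results". The outcome is then stated for "All cases confirmed on repeat testing as meeting criteria A or B" with no other cause found: "Such potential Hy's Law cases should be reported as serious adverse events". The section says nothing about holding or stopping drug, or about DLT status.

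**Section 5.6.** Apart from the hematologic items, a DLT is any other Grade 3 or higher "toxicity not classified under CTCAE blood or bone marrow with the exception of nausea, vomiting, or diarrhea", if at least possibly related to ONC201. There is also a rule without a grade limit: "Any AE leading to inability to complete planned study drug during the DLT window should be considered a DLT". On how events are used, the section says "only those occurring during the defined DLT observation window of treatment (1 cycle) that are considered DLTs will guide dose escalation decisions". Liver injury is not named.

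**Section 6 and Table 6.1.** The table extends to adverse events outside its named list. At Grade 2 or below the dose stays the same; a hold starts at Grade 3. The text leaves modification to the investigator's judgment.

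**Section 9.7.** Severity and seriousness are separate, so serious status does not by itself raise the grade.

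**The concern.** Potential drug-induced liver injury is the one liver signal to which the protocol gives its own section, and a confirmed case is always serious. Yet the two places that turn an adverse event into action, the DLT definition and the dose-modification table, work by grade and do not refer to it. If a case can satisfy Section 9.12.2 while the event is graded 2, following the printed rules means the next dose is given unchanged and the case is not counted in the 3+3 decision.

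Two things are at stake. One is the DLT count, which guides escalation and expansion in Phase 1. The other is continued dosing of a patient with a confirmed liver signal; this applies in every later cycle and in Phase 2 as well.

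**Working it through.** The protocol states no figure on this point to reproduce. The check is of rules, with a little arithmetic.

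**1. Can a qualifying case be Grade 2?** The protocol cites CTCAE v4.03 but does not print its liver limits, so the Grade 2 ceilings are an assumption. For criterion A, the room below Grade 3 is the ceiling minus the entry limit (all in x ULN):

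| Analyte | Entry limit | Assumed Grade 2 ceiling | Room |
|---|---|---|---|
| AST/ALT | 3 | 3 / 4 / 5 / 6 | 0 / 1 / 2 / 3 |
| Bilirubin | 2 | 2 / 2.5 / 3 | 0 / 0.5 / 1.0 |

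The overlap exists for any ceilings above 3 and 2. Alkaline phosphatase must also stay at Grade 2 or below, or be unavailable.

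For criterion B, with b the baseline value, the AST/ALT entry limit is min(max(2b, 3), 8). This gives 3.0 at b = 1.5, 4.0 at b = 2.0 and 5.0 at b = 2.5. The bilirubin limit is min(max(2, b + 1), 3), which gives 2.0 at b = 1.0 and 2.5 at b = 1.5. With an assumed AST/ALT ceiling of 5, the overlap closes once baseline exceeds 2.5.

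**2. Which rule then counts the case?** Relatedness would normally be met, because no other cause has been found. The general Grade 3 rule in 5.6 does not apply. Only the missed-dose rule is left.

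**3. When can a dose still be missed?** Doses fall on Days 1, 8 and 15 (Section 7.3). Taking each possible confirmation day from 1 to 21:

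- If Table 6.1 is followed as printed, no dose is withheld and the case is uncounted on all 21 days.
- If the investigator withholds the next cycle 1 dose after confirmation, a case confirmed on Days 1 to 14 is counted. On Days 15 to 21 (7 days) no dose is left to miss, taking the Day 15 dose as given.

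These are calendar days, not probabilities.

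The in-window chemistry draws after the first dose are on Days 8 and 15. With an assumed laboratory turnaround of r days and the repeat taken 48 hours after awareness, confirmation day = draw day + r + 2 + r:

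| Draw | r = 0 | r = 1 | r = 2 | r = 3 |
|---|---|---|---|---|
| Day 8 | 10 | 12 | 14 | 16 |
| Day 15 | 17 | 19 | 21 | 23 |

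An abnormality in the Day 15 draw can therefore be confirmed after the 21-day window. If the Day 15 dose was given before the result was known, it is also confirmed after the last planned cycle 1 dose. No section requires the result before dosing, although the ± 2 business day visit window would allow an earlier draw.

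**4. Effect of one uncounted case.** 1/3 becomes 0/3, or 2/6, which exceeds the >1/6 de-escalation trigger in Section 3.3, becomes 1/6. This is true of any missed DLT.

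**5. How often?** Section 1.3 reports no drug-related toxicity above Grade 1 in 10 patients dosed every three weeks, and no drug-related adverse events in 9 dosed weekly, all on ONC201 alone. The one-sided 95% upper bound for 0/n is 1 − 0.05^(1/n): 25.9% for n = 10, 28.3% for n = 9, and 14.6% for the 19 pooled across the two schedules. These groups do not supply a rate for the combination.

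**The case against.** The strongest reply is that the protocol already handles such a case through judgment. The investigator may grade the combined event by its maximum intensity (9.7), and Grade 3 would make it a DLT. The dose may be modified (Section 6), the event may be called unacceptable (5.5) or drug stopped for related toxicity (3.1). A withheld Day 8 or Day 15 dose triggers the missed-dose rule. The sponsor hears within 24 hours (9.12.1), Section 10.3 counts discontinuations for treatment-related events, and the Phase 2 dose rests on benefit/risk. The overlap itself depends on grade limits that the protocol does not print.

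Most of this stands, and it keeps the severity low. But apart from the notice, each route depends on discretion or on drug actually being stopped, and none makes the case a DLT or a hold by rule. Section 6 does favor the dose-reducing option when recommendations conflict, but with nothing above Grade 2 there is no conflict.

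A reader might infer that the omission mainly affects cases confirmed after the Day 15 dose. The documents do not support that limit. It holds only if the investigator overrides Table 6.1 earlier in the cycle; followed as printed, the table leaves a Grade 2 case uncounted on any day. Nor do they support the opposite inference, that every Grade 2 case would be dosed through and missed, because the investigator may withhold.

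**Conclusion.** The gap is real but narrow. A potential Hy's Law case graded 2 is serious by rule, yet it becomes a DLT only through a missed cycle 1 dose, and no rule requires that dose to be withheld. After the Day 15 dose that route is closed.

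The conclusion rests on one assumption: Grade 2 ceilings above 3 x ULN for AST/ALT and 2 x ULN for bilirubin. If either value, or the event as a whole, is Grade 3, the existing rule already counts it.

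A reader might want to attach a probability to an uncounted case in Phase 1. The documents give no rate for the combination, and an assumed rate for any Hy's Law case would not measure the smaller set that is graded 2 and uncounted. Frequency is unknown and probably low. This is a low-severity improvement, worth making because the signal is serious and the correction is cheap.

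**What to change.** First check the alkaline phosphatase condition in criteria A and B. As printed, a value of at least 2 x ULN or a missing value qualifies, while a known value below 2 x ULN does not, although the test is in the minimum panel (Table 7.1). Settle this before the DLT definition relies on the criteria.

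Then:

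- Add to Section 5.6: *any potential Hy's Law case under 9.12.2 with onset in the first 21 days, confirmed on repeat testing, regardless of the grade of the individual laboratory values*. Keying it to onset makes clear that a case confirmed on, say, Day 23 still counts.
- Add a line to Table 6.1 that holds ONC201 from the first result meeting the criteria until the 9.12.2 evaluation is complete, and that overrides the row for Grade 2 or below.
- State that a hold for a result not confirmed on repeat is not a DLT. Otherwise the hold could trigger the missed-dose rule.

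The cost is one check of wording and a short amendment, with no extra tests. The downside is that a rare case may expand or stop a cohort that would otherwise have escalated. A hold may also cost one of the three cycle 1 doses, since missed doses are not made up (Section 5.2).
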